Lieu de l'étude	
Partie clinique :
 
Service de Pharmacologie et Toxicologie cliniques, Hôpitaux Universitaires de Genève
 
Analyse des résultats :
 
Unité d'investigations pharmacologiques et toxicologiques, Service de pharmacologie et toxicologie cliniques, HUG
 
Unité de Toxicologie et Chimie Forensiques, Centre Universitaire Romand de Médecine Légale

Calendrier de l'étude	
Début prévu pour octobre 2024 (inclusion des premiers volontaires)
 
Fin prévue pour mars 2025 (dernière session des derniers volontaires)

Déclaration BPEC	Cette étude sera conduite conformément au protocole, aux principes éthiques de la Déclaration d'Helsinki, aux directives internationales ICH-GCP ainsi qu'à la loi suisse sur la recherche humaine (LRH).

Rationnel et Objectifs	
Le cytochrome P450 2C19 (CYP2C19) est l'enzyme responsable du métabolisme de médicaments fréquemment prescrits en clinique comme l'oméprazole, un antiacide inhibiteur de la pompe à proton (IPP), le citalopram, un antidépresseur inhibiteur sélectif de la recapture de la sérotonine (ISRS) ou le clopidogrel, un antiagrégant plaquettaire. Le CYP2C19 présente une importante variabilité interindividuelle de son activité dans la population générale due, notamment, à un fort polymorphisme génétique, avec une trentaine de variants alléliques identifiés à ce jour. Ceci résulte en cinq phénotypes distincts dans son activité : le phénotype métaboliseur lent (PM), le phénotype métaboliseur intermédiaire (IM), le phénotype métaboliseur normal (NM), le phénotype métaboliseur rapide (RM) et le phénotype métaboliseur ultra-rapide (UM).
 
Pour caractériser l'activité du CYP2C19, il existe différentes méthodes de phénotypage à savoir l'administration d'une substance-test métabolisée de manière spécifique par le CYP2C19 et la mesure de paramètres pharmacocinétiques, tels que l'aire sous la courbe (AUC), ou des ratios métaboliques entre les concentrations de la molécule-mère et de son métabolite. Les substances-tests les plus utilisées sont l'oméprazole (OPZ) et la méthénytoïne. Il est également possible de mesurer le phénotype de plusieurs isoformes des CYPs simultanément avec le phénotypage mixte, tel que le « Geneva cocktail » développé aux HUG. Ce dernier est composé de 6 substances-tests permettant de phénotyper simultanément 6 isoformes des CYPs, dont l'OPZ pour le CYP2C19.
 
Malgré une bonne tolérance de ce cocktail, certains patients peuvent être réticents à l'administration de médicaments de manière exogène et il n'est parfois pas possible de les administrer à certains patients (e.g. femmes enceintes, enfants, personnes âgées). Il convient par ailleurs d'attendre 2h après l'ingestion du « Geneva cocktail » avant d'effectuer la prise de sang, ce qui peut poser quelques contraintes pratiques en clinique.
 
L'utilisation de biomarqueurs endogènes de mesure de l'activité des CYPs permettrait ainsi de s'affranchir de ces obstacles et de rendre la pratique moins invasive et plus acceptable pour les patients. Une récente étude consacrée au CYP2D6 conduite au sein de notre service a permis d'identifier de nouveaux biomarqueurs endogènes pour cet isoforme, à savoir la solanidine, un alcaloïde aglycone très commun, et ses dérivés.
 
Le but de notre étude est d'identifier de nouveaux biomarqueurs endogènes pour mesurer (phénotyper) l'activité du CYP2C19 par métabolomique non ciblée.
 
Les volontaires sains seront stratifiés en deux groupes selon leur phénotype pour le CYP2C19 : les sujets PMs et NM-RMs-UMs. Les sujets IMs seront exclus afin d'observer des différences plus significatives au sein des deux groupes.
 
Objectif primaire :
 
 - Partie 1 : mise en évidence de potentiels substrats et/ou métabolites endogènes du CYP2C19 par métabolomique non ciblée sur des échantillons urinaires, plasmatiques et de vésicules extracellulaires dérivées du foie prélevés avant (baseline, session 1) et après administration répétée de fluvoxamine (inhibition enzymatique du CYP2C19, session 2) ainsi qu'après administration répétée de rifampicine (induction enzymatique du CYP2C19, session 3). - Partie 2 : identification des substrats et/ou métabolites endogènes du CYP2C19 parmi les composés mis en évidence dans la partie 1 par analyse semi-quantitative ciblée sur des échantillons urinaires, plasmatiques et de vésicules extracellulaires dérivées du foie des volontaires sains PMs et NM-RMs-UMs à la baseline (i.e sans administration préalable de fluvoxamine ou de rifampicine). 
Objectifs secondaires :
 
 - Identification des substrats et/ou des métabolites endogènes du CYP2C19 à l'aide de bases de données internes ou externes, par fragmentation en LC-MS/MS ou à l'aide de standards de référence. - Corrélation des concentrations plasmatiques et/ou urinaires et/ou de vésicules extracellulaires dérivées du foie d'un substrat et/ou un métabolite endogène du CYP2C19 avec le phénotype (ratio sanguin OH-oméprazole/oméprazole) et/ou le génotype du CYP2C19.
-------------------------------	---

	
 - Évaluation des niveaux d'expression de cfRNA du CYP2C19 issu de vésicules extracellulaires et corrélation avec le génotype, phénotype (omeprazole) et modulation de l'activité du CYP2C19 par administration d'un inhibiteur (fluvoxamine) et d'un inducteur (rifampicine). - Comparer la signature métabolomique du CYP2C19 des vésicules extracellulaires dérivées du foie avec celle du plasma et de l'urine. - Comparer la signature métabolomique du CYP2C19 des vésicules extracellulaires dérivées du foie avec celle des vésicules extracellulaires totales. - Construction d'un modèle de régression linéaire multiple pour prédire le phénotype du CYP2C19. - Validation des résultats à l'aide d'enzymes recombinantes et d'hépatocytes humains génotypés pour le CYP2C19.
Méthode	
Le projet consiste en trois parties expérimentales :
 
 - Partie 1 : mesure de l'impact d'un inhibiteur du CYP2C19, la fluvoxamine, sur le métabolome urinaire, plasmatique et de vésicules extracellulaires dérivées du foie - Partie 2 : mesure de l'impact d'un inducteur du CYP2C19, la rifampicine, sur le métabolome urinaire, plasmatique et de vésicules extracellulaires dérivées du foie - Partie 3 : mise en évidence des biomarqueurs du CYP2C19 par mesure de l'impact des polymorphismes du CYP2C19 sur les composés affectés dans les parties 1 et 2. 
Il s'agit d'une étude ouverte à design croisé chez des volontaires sains répartis en deux groupes selon leur génotype du CYP2C19 (PMs et NMs-RMs-UMs). Trois sessions auront lieu pour chaque sujet :
 
Session 1 : prélèvements plasmatique et urinaire ainsi que la détermination du ratio sanguin OH-oméprazole/oméprazole à la baseline par prise de sang capillaire.
 
Session 2 : idem session 1 avec prise au préalable de 50 mg de fluvoxamine pendant 7 jours consécutifs (inhibiteur fort du CYP2C19).
 
Session 3 : idem session 1 avec prise au préalable de 600 mg de rifampicine pendant 10 jours consécutifs (inducteur fort du CYP2C19).
 
A chaque session, une récolte urinaire sur 24h est effectuée, suivie d'une prise de sang veineux (6 x 6 ml) le matin à jeun. Le phénotypage a ensuite lieu avec la prise d'oméprazole à 10 mg, suivie d'une prise de sang capillaire (4 x 10 µl) après 2h. Après la session 1, la prise de fluvoxamine a lieu durant 7 jours consécutifs (administration au total de 7 doses de fluvoxamine à 50 mg), pouvant commencer au moment du repas de midi lors du déroulement de la session 1. La dernière prise de fluvoxamine doit avoir lieu 2h avant l'administration d'oméprazole à 10 mg lors de la troisième visite (jour 11±4j, session 2). Enfin, la prise de rifampicine aura lieu au moins 6 jours après la session 2, tous les soirs durant 10 jours consécutifs (administration au total de 10 doses de rifampicine à 600 mg). La dernière prise de rifampicine doit avoir lieu le soir de la veille de l'administration d'oméprazole à 10 mg lors de la quatrième visite (jour 27±4j, session 3).

Nombre de volontaires	40 volontaires sains : 10 PMs et 30 NMs-RMs-UMs
Durée de l'étude	Au minimum 24 jours et au maximum 32 jours par volontaire

[figure not shown]
Critères de sélection	
Critères d'inclusion :
 
Hommes et femmes en bonne santé habituelle Age : entre 18 et 65 ans IMC : entre 18 et 27 Capables de donner leur consentement éclairé Compréhension de la langue française Génotype du CYP2C19 : PMs, NM_s, RM_s ou UM_s Au moins une contraception à effet barrière pendant toute la durée de l'étude et 1 mois après la fin de l'étude (en plus de la contraception hormonale habituelle le cas échéant)
 
Critères de non-inclusion :
 
Génotypes IM_s du CYP2C19 Participation à un autre essai clinique interventionnel dans les 3 mois précédent l'inclusion Femme enceinte ou allaitante Pathologies, médicaments ou aliments qui affectent l'activité des CYP450 Antécédent de transplantation hépatique Fumeurs réguliers de ≥ 10 cigarettes/jour Altération des tests hépatiques (ASAT, ALAT, GGT, bilirubine plus de 3x la norme) Insuffisance rénale (urée sérique, créatinine sérique et eGFR en dehors des normes) Antécédent d'alcoolisme chronique ou d'abus de substances psychotropes Allergie aux médicaments administrés Pathologie psychiatrique active Score de Beck ≥ 10 (question sur le suicide > 0) Prise d'alcool 2 jours avant la session 1 et pendant la prise de fluvoxamine et rifampicine Porteurs de lentilles de contact

Produit d'étude Dosage Voie d'administration Durée du traitement	
Oméprazole Spécialité : Antramups® Dosage : prise unique d'un comprimé de 10 mg d'Antramups® le matin à chaque session de phénotypage Voie d'administration : orale Durée de traitement : prise unique, à chaque session Dose thérapeutique habituelle : 20-40 mg/j, selon l'indication
 
Fluvoxamine Spécialité : Floxyfral® junior cpr pell 50 mg Dosage : un comprimé de 50 mg de Floxyfral® junior avec le petit déjeuner pendant 7 jours (le dernier jour de prise étant au matin du phénotypage de la session 2, 2 h avant la prise d'oméprazole) Voie d'administration : orale Durée de traitement : 7 jours consécutifs (7 comprimés au total) Dose thérapeutique habituelle : Dose initiale de 50 mg par jour, puis titration jusqu'à 100 mg 1x/j-150 mg 2x/j
 
Rifampicine Spécialité : Rimactan®, caps 300 mg Dosage : 600 mg/j, soit 2 capsules de 300 mg le soir pendant 10 jours (le dernier jour de prise étant le soir de la veille précédent le phénotypage de la session 3) Voie d'administration : orale Durée de traitement : 10 jours consécutifs (20 comprimés au total) Dose thérapeutique habituelle : 600-1200 mg/j selon l'indication

Critères d'évaluation	
Critère d'évaluation principal :
 
Changement des intensités des ions déterminées par spectrométrie de masse selon le génotype (PMs versus NM_s-RM_s-UM_s) et selon les sessions. Les ions montrant un changement de facteur $\geq 1,5$ ou $\leq 0,67$ seront qualifiées de

	
biomarqueurs endogènes du CYP2C19. Les signaux chromatographiques seront détectés dans l'urine, plasma et vésicules extracellulaires dérivées du foie de volontaires sains par chromatographie liquide couplée à la spectrométrie de masse à haute résolution (LC-HRMS) à chaque session pour chacun des volontaires.
 
Critères d'évaluation secondaires :
 
Corrélation du phénotype avec les métabolites statistiquement significatifs mesurés en métabolomique.
 
Modèle de régression linéaire multiple pour prédire le phénotype du CYP2C19.

Evaluation de la tolérance	Les SAEs avec issue fatale et les SUSARs seront systématiquement relevés et rapportés dans les délais appropriés à la CCER et aux autorités.
Méthode statistique	
Critères primaires :
 
Analyses univariées : Volcano plot
 
Analyses multivariées : Analyse en composantes principales, régression des moindres carrés partiels
 
Critères secondaires :
 
Test de corrélation de Spearman

STUDY FLOWCHART

*The first tablet of fluvoxamine can be administrated during lunch on day 1 of session 1

STUDY DESIGN

Abbreviations

ADR	adverse drug reaction
AE	adverse event
ALAT	alanine-aminotransferase
ASAT	aspartate-aminotransferase
ASR	annual safety report
AUC	area under the concentration curve
CCER	commission cantonale d'éthique et de la recherche
eCRF	electronic case report form
CYP	cytochrome P450
DBS	dried blood spot
DDI	drug-drug interaction
EV	extracellular vesicle
FDA	US Food and Drug Administration
GGT	Gamma glutamyl transpeptidase
HUG	Geneva University Hospitals
IM	intermediate metabolizer
MR	metabolic ratio
NM	normal metabolizer
NMR	nuclear magnetic resonance
OClin	swiss ordinance on clinical trials on research involving humans
OH-OPZ	hydroxyomeprazole
OPZ	omeprazole
PM	poor metabolizer
RM	rapid metabolizer
SAE	serious adverse event
SUSAR	suspected unexpected serious adverse reaction
UM	ultra-rapid metabolizer
UMR	urinary metabolic ratio

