5.1.2 Fluvoxamine: CYP2C19 inhibitor

Fluvoxamine is an antidepressant drug of the selective serotonin reuptake inhibitor (SSRI) class. It is used as a medical treatment in depression, as well as in anxiety disorders. The usual starting dose of fluvoxamine is 50 mg per day. The daily dose can be increased to 100 mg once a day and up to a maximum of 300 mg per day taken in divided doses (e.g. 150 mg twice a day) for non-responding patients.⁴⁷ In this study, the dose administered is 50 mg once a day for 7 days.

Following oral administration, fluvoxamine is rapidly and almost completely absorbed in the gastrointestinal tract. However, it is also subject to hepatic first-pass metabolism, resulting in an absolute bioavailability of 53%. Steady-state maximal concentrations are reached between 10 to 14 days.⁴⁷⁻⁴⁹ Fluvoxamine is extensively metabolized in the liver by CYP2D6 and CYP1A2 to at least 11 different metabolites, of which no one is known to be pharmacologically active.⁵⁶⁻⁵⁹ These metabolites are widely eliminated in urine, with a variable fluvoxamine elimination half-life of about 19,5 hours (range 17-22 hours) after multiple intakes.⁴⁷⁻⁴⁹ Adverse effects of fluvoxamine are those of SSRIs, which include asthenia, tremor, somnolence, insomnia, gastro-intestinal disorders and erectile dysfunction. In patients suffering from depression, a deterioration of the depressive symptoms and/or suicidal ideation or behaviours may appear with fluvoxamine intake.⁴⁷ Consequently, subjects with any psychiatric disorders

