5.1.3 Rifampicin: CYP2C19 inducer

Rifampicin is rifamycin antibiotic used to treat infections such as tuberculosis, leprosy, meningitis, and staphylococcal infections. The usual dose of rifampicin depends on the type and severity of the infection being treated, as well as the patient's age, weight, and other medical conditions. The standard adult dose ranges from 600 to 1200 mg per day.⁶⁴⁻⁶⁶ In this study, the dose administered is 600 mg (i.e. 2 tablets of 300 mg) once a day in the evening for 10 days.

Following oral administration, rifampicin is rapidly and almost completely absorbed. Food intake can reduce the absorption of rifampicin. Consequently, it is usually taken 1 hour before or 2 hours after a meal. Steady-state maximal concentrations are reached within 7 days.⁶⁴⁻⁶⁷ Rifampicin is extensively metabolized in the liver to the active compound 25-O-desacetylrifampicin, which is further metabolized into inactive compounds.^{64-66,68} These metabolites are primarily excreted in the bile (80%), with a small amount eliminated in the urine (4-18%). Rifampicin elimination half-life is dose-dependent and is approximately 1 to 2 hours after multiple doses of 600 mg per day.^{64,69} Common adverse effects of rifampicin include gastrointestinal disturbances like nausea, vomiting and diarrhoea as well as flu-like symptoms such as fever, chills and headache. These adverse effects are generally mild and resolve once

the medication is discontinued. In addition, rifampicin is responsible of staining contact lens (in addition of urine, sweat, sputum and tears), from which contact lens wearers are excluded from the study. Because Rifampicin is contraindicated in case of severe renal impairment, renal tests (i.e. serum urea, serum creatinine and eGFR) were included during the initial screening procedure of this study in order to exclude all renal impairment cases.

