7.2 Adverse events collection and grading

Drugs used in this study are approved in Switzerland and their security profile is well known. Therefore, AEs of grade ≥ 2 , SAEs and SUSARs are unlikely. If that were to happen, only SAEs that result in death and SUSARs would be reported in the eCRF.

AE monitoring and filling out of the eCRF for each participant begins when they receive omeprazole during the second visit (session 1). This monitoring will continue throughout the two-hour duration of the visit and the same procedure will be followed for the third visit (session 2) and the fourth visit (session 3). To ensure comprehensive safety monitoring, a follow-up phone call will be conducted two days after each visit, including the fourth one (final safety follow-up). This allows for the early detection of any potential AEs related to fluvoxamine and rifampicin, as well as adverse events that may appear after the study. Participants will be encouraged to contact study investigators at any time if they experience an AE, even if it occurs after the study has ended. This is particularly important if the participant feels they need to discontinue the medication during the study or if they require medical assistance.

The eCRF report will document the reasons for notification (e.g. death, life-threatening event), the date of first occurrence, and a description of SAEs/SUSARs. The report will also assess the nature of the SAE (expected or unexpected) and its relationship to the study drug (imputability) to determine if it qualifies as a SUSAR. Additionally, information on any potentially responsible medications will be recorded.

All AEs, SAEs and/or SUSARs will be followed up until the event is resolved. The SAEs that are not reported in the eCRF and AEs of grade ≥ 2 will be recorded in the electronic medical records of HUG for each study subject by the investigator.

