8. QUALITY CONTROL AND ASSURANCE

8.1 Data handling and record keeping/archiving

8.1.1 eCRF

The electronic Case Report Form (eCRF) is an investigator file, written for each study subject, which contains data necessary to the progress and the analysis of the study, including safety data.

In this study, the following data will be entered in the eCRF using the browser-based software REDcap :

- Review of inclusion and non-inclusion criteria (check boxes) *
- Demography: gender*, age*
- Concomitant medication(s)*
- weight*, size* and BMI*
- CYP2C19 genotype and phenotype
- For women: date of last menstrual cycle, contraception methods and pregnancy test result at each visit*
- Time of drug intakes*
- Time of venous and capillary blood samplings*
- Time of urine collections*
- SAE resulting in death and SUSARs*

All items followed by an asterisk will be entered directly in the eCRF and will be considered source documents.

Each page will include the subject's and visit's number as well as all the modifications dated and signed by the investigator.

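### The synopsis, 7.2 and 8.1.1 limit the tolerance data to fatal SAEs and SUSARs while 7.4 says otherwise, leaving expected drug reactions without a settled place in the trial database

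*Protocol*

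**What the plan says.** Three places in the protocol set one limit:

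- The synopsis, in the row on evaluation of tolerance: "Les SAEs avec issue fatale et les SUSARs seront systématiquement relevés et rapportés dans les délais appropriés". The sentence goes on to name the ethics committee and the authorities as recipients.
- Section 7.2: "only SAEs that result in death and SUSARs would be reported in the eCRF". It places the remaining SAEs elsewhere, and "AEs of grade ≥ 2 will be recorded in the electronic medical records of HUG".
- Section 8.1.1 describes the eCRF as holding "data necessary to the progress and the analysis of the study, including safety data". The only adverse-event item in its list is "SAE resulting in death and SUSARs".

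Section 7.4 points the other way. An AE found at a visit or phone call, or reported by the volunteer at any time, is to be documented in the eCRF, with no limit on grade or expectedness.

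The protocol also names the reactions it foresees. Section 5.1.3: "Common adverse effects of rifampicin include gastrointestinal disturbances like nausea, vomiting and diarrhoea as well as flu-like symptoms". Section 5.1.2: "Adverse effects of fluvoxamine are those of SSRIs, which include asthenia, tremor, somnolence", followed by insomnia, gastrointestinal disorders and erectile dysfunction.

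Neither the endpoints (3.2) nor the data analysis section (9.2) mentions a safety summary.

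**The concern.** The harms that the protocol foresees are expected and mostly non-fatal. A tolerance evaluation confined to fatal SAEs and SUSARs is built to leave such events out. The investigator will still grade, treat, follow and record them, but under 7.2 and 8.1.1 in individual hospital files rather than in the database that 8.1.1 describes as serving the analysis. The transfer described in 8.1.2 runs from the eCRF to the hospital record; none is described in the other direction.

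At stake is whether the trial can say, from its own data, how many healthy volunteers had a reaction of at least moderate grade during the fluvoxamine course and how many during the rifampicin course. According to 10.2, neither drug has an indication in these people, so harm is the only individual clinical effect to weigh. The reason given in 7.2 for the narrow collection is that such events are unlikely, and no rate supports it.

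**Working it through.** No figure in the protocol is at issue, so there is none to reproduce. The check sets the texts side by side and then gives a scale.

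**Step 1. Where each kind of event goes.**

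| Event | Under the synopsis, 7.2 and 8.1.1 | Under 7.4 |
|---|---|---|
| Fatal SAE | eCRF | eCRF |
| SUSAR | eCRF | eCRF |
| Non-fatal SAE that is not a SUSAR | hospital record | eCRF |
| Non-serious AE of grade ≥2 | hospital record | eCRF |
| Grade 1 AE | no place named | eCRF |

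The texts agree on the first two rows and disagree on the rest. The reactions named in 5.1.2 and 5.1.3 fall, as a rule, in the last three rows.

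**Step 2. Can a named reaction count as a SUSAR?** Under 7.1 a SUSAR must be serious, at least possibly related to the drug, and not expected. Not expected covers an event not described before, or known at a lower frequency. An unexpected drug reaction is one that does not fit the official product information. A serious form of a named reaction can therefore qualify if its severity or frequency goes beyond what is labelled. A hospitalised reaction of labelled kind, severity and frequency would not qualify, and if non-fatal it would stay outside the eCRF under 7.2.

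**Step 3. Other routes.** Section 3.5 keeps a list with the date and reason for drop-out. This shows a reaction only when it ends participation; a volunteer who reacts and completes leaves no trace there. Section 7.3 sends AEs of special interest to the regional pharmacovigilance centre, but the text lists no such events. It also requires an annual safety report, whose content is not described.

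**Step 4. Denominator.** Withdrawn volunteers are replaced (4.5, 9.3), although their data up to withdrawal are kept and analysed (5.5). A count over the 40 completers would leave out people who stopped because of a reaction. The natural denominator for each drug is everyone who took at least one dose of it.

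**Step 5. Scale.** Section 3.1 gives 40 volunteers. The protocol gives no AE rate, so the share p of volunteers with an expected grade ≥2 reaction is an assumption. Expected number = 40 × p. Chance of at least one = 1 − (1 − p)^40, with volunteers taken as independent.

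| Assumed p | Expected volunteers | Chance of at least one |
|---|---|---|
| 1% | 0.4 | 33% |
| 5% | 2 | 87% |
| 10% | 4 | 98.5% |
| 20% | 8 | >99.9% |

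Under 7.2 and 8.1.1 none of these volunteers' reactions would be in the eCRF unless fatal or a SUSAR. Under 7.4 they would be.

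**The case against.** The strongest reply is section 7.4. It does route detected events to the eCRF, and 8.1.1 says that the eCRF serves the analysis. A reader might infer from the synopsis and 7.2 that expected reactions will appear in no trial result; the documents do not support that. It would follow only if 7.2 prevails over 7.4, and the protocol does not say which prevails. The final report (10.3) and the annual safety report (7.3) are also required, and nothing limits their content to fatal SAEs and SUSARs.

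Second, an AE table is ordinary material for a statistical analysis plan, which is not shown. That is right, and silence in 9.2 alone would be no finding. The point rests on what the protocol states: which events enter the database. An analysis plan cannot tabulate by drug period what the database does not hold, short of going back to the hospital files.

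Third, the synopsis sentence is partly a rule on reporting to authorities, and tolerance is neither an objective nor an endpoint. This also stands, but the row is headed as the evaluation of tolerance, and 7.2 and 8.1.1 carry the same limit into data collection.

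Fourth, 7.2 calls grade ≥2 AEs unlikely and 5.1.3 calls rifampicin reactions generally mild. That may be so, and the 1% row allows for it.

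Two further inferences should not be drawn. The higher omeprazole exposure of PMs (2.3) does not support a PM difference in tolerability here: omeprazole is a single 10 mg dose per session with adverse effects called highly unlikely (5.1.1), fluvoxamine is attributed to CYP2D6 and CYP1A2 (5.1.2), and no CYP2C19 route is named for rifampicin (5.1.3). Nor should zero fatal SAEs and SUSARs in 40 volunteers be set against an assumed risk of grade ≥2 AEs. These are different events, and the protocol nowhere says that one would be read as the other.

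**Conclusion.** The concern holds as an inconsistency with a conditional consequence. The synopsis, 7.2 and 8.1.1 confine the stated tolerance evaluation and the eCRF item list to fatal SAEs and SUSARs; 7.4 contradicts them. If the first three govern, non-fatal expected reactions fall outside the tolerance evaluation, with the exception in step 2 for serious reactions that become unexpected. The trial database could then not give their number by drug period.

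The size cannot be fixed from the document. The range of 0.4 to 8 affected volunteers rests wholly on assumed rates of 1% to 20%, and its low end fits the protocol's own expectation best. No effect on the metabolomic endpoints is claimed. The sponsor should make the change because it is cheap and gives a fuller account of harm in healthy volunteers.

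**What to change.** Reconcile the synopsis row on tolerance, 7.2, 7.4 and the item list in 8.1.1 so that they name the same events. All SAEs, and the AEs of grade ≥2 already recorded under 7.2, should be entered in coded form in the eCRF.

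State in the synopsis row and in 9.2 that these events are summarised descriptively: number and percentage of volunteers, by CTCAE grade, causality category (7.1) and drug period. The denominator for each drug is every volunteer who took at least one dose of it, including those withdrawn and replaced.

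Expedited reporting to the ethics committee and Swissmedic stays as it is, as does clinical handling of events. No visit, test or call is added. The cost is some wording, the transcription of events already graded for about 40 volunteers, and one descriptive table. The safety statement may also turn out less favourable than one limited to fatal SAEs and SUSARs.
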